**Primary PD Biomarker:**

- Neopterin

**Primary PD Assessments:**

- Area under the effect curve (AUEC) change from baseline truncated after return to baseline
- Percentage area under the effect curve (pAUEC) change from baseline truncated after return to baseline
- Maximum change from baseline at single time-point

**Secondary PD Assessments:**

- MxA
- Modeling-based measures using multiple doses
  - Maximum PD response (Emax)
  - Concentration that gives half maximal response (EC50)

**Exploratory PD Biomarkers:**

- Plasma proteomics (assessment of circulating proteins including MxA levels)
- Plasma small RNA transcriptomics (assessment of circulating small RNAs)

**Safety Assessments:**

Safety will be evaluated in terms of adverse events (AEs), clinical laboratory results (hematology, serum chemistry, and urinalysis), vital sign measurements (blood pressure, heart rate, respiratory rate, and oral body temperature), safety 12-lead ECG results, and physical examination findings.

**Other Assessments:**

Buffy coat samples will be collected and processed for genomic analyses. Maintenance of privacy of the genetic information of study subjects is a priority. All DNA samples will be de-identified. DNA may be stored and used for analyses for up to 10 years.

Urine samples will be collected and sample analysis will be performed by DARS research staff.

**Sample Size and  
Threshold Determination:**

Approximately 84 healthy subjects are planned for enrollment, of which 72 will be randomized to one of 6

different active treatment arms (i.e. 12 per treatment arm) and 12 will be randomized to placebo. The sample size was determined empirically. Twelve subjects per arm was deemed adequate for the pharmacokinetic and pharmacodynamic assessments in this study.

### **Statistical Methods:**

All data will be presented in data listings. Data from subjects excluded from an analysis population will be presented in the data listings but not included in the calculation of summary statistics. The number of subjects who enroll in the study and the number and percentage of subjects who complete each assessment will be presented. The frequency and percentage of subjects who withdraw or discontinue from the study and the reason for withdrawal or discontinuation will be summarized. Demographic and baseline characteristics will be summarized overall and by treatment for all subjects.

Descriptive statistics will be used to summarize demographic and baseline subject characteristics. For continuous variables, the mean, median, standard deviation (SD), minimum, and maximum values will be reported. For categorical (nominal) variables, the number and percentage of subjects (or observations) will be reported.

**PD and PK:** The PD and PK populations will include all subjects who receive study drug and have at least 1 estimable PD and PK parameter after dosing. PD and PK parameters of Avonex or Plegridy will be listed and summarized using descriptive statistics (n, geometric mean, coefficient of variation, minimum, median, and maximum).

### **Primary Analysis**

#### **Pharmacodynamics**

##### **Neopterin and MxA protein**

AUEC will be calculated for each subject. For each dose, separate intervals will be used for the AUEC assessment to truncate noise introduced from baseline fluctuations.

Maximum decrease from baseline will be determined from all sampled timepoints. For both assessments and biomarkers, measures will be log-transformed and utilize an ANCOVA approach for calculating geometric means and 90% confidence intervals for each treatment.

Separate population PD analyses will be conducted using nonlinear mixed effect modeling with NONMEM. AUECs calculated for each subject from all doses for a drug and

placebo patient will be combined and evaluated assuming a saturating  $E_{\max}$  relationship to characterize system parameters such as  $E_{\max}$  and  $EC_{50}$ .

Other biomarkers will be collected at the same timepoints and time-course data will be analyzed for each subject using similar approaches as part of exploratory analyses.

**Pharmacokinetics:** Maximum observed plasma concentration ( $C_{\max}$ ) and area under the plasma concentration-time curve (AUC) are the primary PK parameters of interest in PK similarity studies with extravascular drug administration. These and additional PK parameters (i.e.,  $t_{\max}$ , half-life, elimination rate) will be determined for each subject using non-compartmental methods. All parameters will be reported with standard descriptive statistics including the geometric mean and coefficient of variation. Calculation of PK parameters will be performed using actual sampling times.

### **Safety**

The safety population will include all subjects who receive at least 1 dose of any of the study drugs. Any AEs will be coded using the Medical Dictionary for Regulatory Activities (MedDRA). The incidence of AEs, organized by system organ class and preferred term, will be summarized with a focus on treatment-emergent AEs. Vital sign measurements will be summarized using descriptive statistics by time point. All values will be evaluated for clinically notable results. Data for additional safety parameters (e.g., physical examination findings) will be listed.

**Date of Protocol:** 17 August 2020

## 1. List of Abbreviations

Abbreviation	Definition
AE	adverse event
Ag/Ab	antigen/antibody
AUC	area under the plasma concentration-time curve
CDC	Centers for Disease Control and Prevention
CFR	Code of Federal Regulations
C max	maximum observed plasma concentration
COVID-19	coronavirus disease of 2019
ECG	electrocardiogram
eCRF	electronic case report form
FDA	Food and Drug Administration
GCP	Good Clinical Practice
HBsAg	hepatitis B surface antigen
HepC	hepatitis C
HIPAA	Health Insurance Portability and Accountability Act
HIV	Human immunodeficiency virus
ICH	International Council for Harmonisation
IRB	Institutional Review Board
IV	intravenous
NSAID	nonsteroidal anti-inflammatory drug
PD	pharmacodynamic
PK	pharmacokinetic
QA	quality assurance
SAE	serious adverse event
SARS-CoV-2	severe acute respiratory syndrome coronavirus 2
SD	standard deviation
TEAE	treatment-emergent adverse event
T max	time of C max

## **2. Introduction**

Per statute, biosimilarity is defined when the biologic product “is highly similar to the reference product notwithstanding minor differences in clinically inactive components” and “there are no clinically meaningful differences between the biological product and the reference product in terms of the safety, purity, and potency of the product” (Public Health Service Act, Section 351(i)(2)). Biosimilars approved to date have generally included comparative clinical outcome studies. These typically require large sample sizes and long study length. However, FDA guidance documents outline that biosimilars may be approved based on clinical pharmacology pharmacokinetic (PK)/pharmacodynamic (PD) biomarker data without a comparative clinical study that contains an efficacy endpoint. FDA guidance outlines general principles for a PD biomarker; however, an evidentiary framework for acceptance and evaluation of PD biomarkers to support biosimilar approval does not exist.

To support a determination of biosimilarity based on clinical pharmacology studies, FDA guidance states that clinical PK and PD studies should be conducted in the most sensitive and informative population. This should generally be healthy subjects if the product can be safely administered to them and a PD response is observed, as there is generally less variability. In addition, the most sensitive dose should be selected to detect and evaluate differences in the PK and PD profiles between products, which will usually be a dose on the steep part of the dose-response curve. Of note, for many biologics the approved dose is a super-saturating dose on the flat part of the dose-response curve. This highlights the potential need for studying doses that may be substantially lower than the approved clinical dose. Thus, FDA guidance recommends performing a pilot study with the reference product to determine an optimally informative dose.

Furthermore, FDA’s guidance states that a small pilot study can evaluate the PK/PD relationship at multiple dose levels (e.g. low, intermediate, and clinical (i.e., high) doses) to obtain dose-/exposure-response data. If multiple dose levels are studied, PK/PD parameters such as the maximum PD response ( $E_{max}$ ), the concentration that gives-half maximal response ( $EC_{50}$ ) and the slope of the concentration-effect relationship should be evaluated for similarity to further reduce uncertainty, though the evidentiary framework for comparing model-based assessments of PD similarity still needs to be developed.

### **2.1. Interferon beta-1a Products**

The products (interferon beta-1a [Avonex] and peginterferon beta-1a [Plegridy]) were approved for the treatment of patients with relapsing forms of multiple sclerosis. Interferon-beta is part of the normal immediate immune system response to viral infections. Binding of interferon-beta to its receptor initiates a complex signaling system that ultimately leads to over 1000 genes being up or down regulated. The precise mechanism by which the drug modulates the disease process has not been described. As

multiple sclerosis is an autoimmune disease, the ability of interferon-beta to modulate immune system responses is likely to be a key part of its mechanism of action.

Both drugs were approved based on randomized, double-blind, and placebo-controlled studies in patients with relapsing forms of multiple sclerosis. The primary endpoint for these products was time to progression in disability, measures as an increase in the Kurtzke Expanded Disability Scale for at least 1 point sustained for at least 6 months (interferon beta-1a) and annualized relapse rate over 1 year (peginterferon beta-1a). There is limited data on the biomarkers influenced by administration of these products, and even less information on the dose-response relationship between changes in the biomarkers and drug dose. While one single biomarker is not expected to describe effects from interferon products, the hypothesis is that understanding changes in multiple, non-overlapping pathways, and showing similarity on multiple biomarkers may provide a pathway for PK/PD-based similarity assessments for these products in lieu of dedicated non-inferiority efficacy studies.

## **2.2. Summary**

This study will obtain data over a range of doses, including information on the steep part of dose-/exposure-response curve, to inform clinical trial operating characteristics of subsequent PK and PD similarity studies for these drugs. This would be similar to and could substitute for what is suggested as a pilot study in the existing FDA biosimilars guidance. The study will collect data on various PD markers to better understand the dose-response relationship and variability in healthy subjects of traditional PD measurement-based approaches at a single dose (e.g. AUEC and maximal response at a single time point). The study will also evaluate use of model-based approaches for analyzing data from the various dose levels to inform dose selection for similarity studies. In addition, as many biologics from other classes do not have biomarkers associated with the known mechanism-of-action, this study will explore the use of proteomics and small RNA transcriptomics, and the analytical approach needed to identify and characterize circulating biomarkers that could be used for a PD similarity assessment.

## **3. Study Objectives**

### **3.1. Primary Objective**

The primary objective of this study is:

1. To inform clinical trial operating characteristics for future clinical pharmacology PK and PD similarity studies using the different biomarker-based approaches.

### **3.2. Secondary Objectives**

The secondary objectives of this study are:

1. To determine the values and variability of PK and PD characteristics at three dose levels (i.e., low, intermediate, and high doses).
2. Explore PK and PD relationships using appropriate models

### **3.3. Exploratory Objective**

The exploratory objective of this study is:

1. To evaluate the utility of circulating proteins and small RNAs as potential PD biomarkers.
2. To inform on the analytical approach and experimental design needed for identifying exploratory proteomic- and RNA-based PD biomarkers in plasma

## **4. Study Endpoints**

### **4.1. Primary Endpoint**

The primary endpoint of this study is:

1. The values and variability of standard PD metrics (AUEC and maximal difference at a single time-point) for neopterin at low, intermediate, and high doses of interferon beta-1a and peginterferon beta-1a.

### **4.2. Secondary Endpoints**

The secondary endpoints of this study are:

1. The values and variability of standard PD metrics (AUEC and maximal difference at a single time-point) for MxA at low, intermediate, and high doses of interferon beta-1a and peginterferon beta-1a.
2. The values and variability of pharmacokinetic characteristics ( $C_{max}$  and AUC of free drug concentration) at low, intermediate, and high doses of interferon beta-1a and peginterferon beta-1a.
3. Parameters ( $E_{max}$ , and  $EC_{50}$ ) calculated by the model after combining data from low, intermediate, and high doses of interferon beta-1a and peginterferon beta-1a with placebo data.

### **4.3. Exploratory Endpoints**

The exploratory endpoints of this study are:

1. Plasma proteomics (differential expression of circulating proteins)
2. Plasma small RNA transcriptomics (differential expression of circulating small RNAs)

## 5. Investigational Plan

### 5.1. Study Design

This is a randomized, placebo-controlled, single-dose, parallel arm study. Healthy subjects will be randomized to three dose groups (low, intermediate, and high) of each drug (interferon beta-1a [Avonex] and peginterferon beta-1a [Plegridy]) or placebo (see Table 5-1).

Subjects will report to the study site for screening assessments from days -21 to -2 and then will return to the site on day -1 for baseline assessments. Prior to and following study drug or placebo administration on day 1, they will undergo assessments as described in Table 9-1. Subjects randomized to Treatment Groups A-C will stay in house for the duration of the study and will be discharged on Day 7. Subjects randomized to Treatment Groups D-G will stay in house for the duration of the study and will be discharged on Day 14. Each treatment group should include equal representation of male and female subjects.

Depending on the treatment arm, subjects will have up to a maximum of 20 PK and PD blood draws and additional study procedures as outlined in the schedule of events.

**Table 5-1: Study Treatment Groups**

Subjects (n)	Treatment Group	Drug
12	A	Interferon beta-1a (Avonex) low (7.5 µg)
12	B	Interferon beta-1a (Avonex) intermediate (15 µg)
12	C	Interferon beta-1a (Avonex) high (30 µg)
12	D	Peginterferon beta-1a (Plegridy) low (31.25 µg)
12	E	Peginterferon beta-1a (Plegridy) intermediate (62.5 µg)
12	F	Peginterferon beta-1a (Plegridy) high (125 µg)
12	G	Placebo

#### 5.1.1 Common Procedures

At the study clinic (Spaulding Clinical Research unit in West Bend, Wisconsin), subjects will be screened for study eligibility from Day -21 to Day -2. On Day -1, subjects will enter the study clinic for check-in procedures the day before study drug administration. During the screening visit, the inclusion and exclusion criteria will be reviewed to ensure the subject is appropriate for the study. The informed consent form will be reviewed with the subject by a member of the study team and the subject will be encouraged to ask

questions to ensure the subject has a good understanding of the study. If the subject is eligible and agrees to participate, the subject will be asked to sign the informed consent form before any study-specific procedure is performed, including randomization.

After the consent process is complete, demographic data, medical history, and concomitant medications (including over-the-counter and complimentary/alternative supplements) will be recorded. A physical examination will be performed by a study team member. Clinical laboratory tests (hematology, serum chemistry, and urinalysis) will be performed. Female subjects must have a negative pregnancy test result. Any values outside the reference range will be evaluated for clinical significance. If a value is determined to be clinically significant or the subject has a positive pregnancy test result, the subject will be instructed to follow-up with his or her personal physician. Screening tests will be performed within 28 days of and no later than 1 day before Day 1.

Screening procedures will be performed by clinic staff, and all screening results will be evaluated by the study clinician/investigator against the inclusion/exclusion criteria to confirm subject eligibility. At check-in, eligibility criteria will be reviewed, any changes in medical history (including concomitant medications) will be documented, vital sign measurements and a 12-lead ECG will be performed, clinical laboratory, drug and alcohol, and pregnancy tests (for females) will be performed, an intravenous (IV) catheter may be inserted into the subject's forearm region for blood collection (if needed), study drug will be administered, and blood samples will be collected per protocol.

The FDA project biostatistician will prepare the randomization schedule, and subjects will be randomly assigned to 1 of 7 treatment groups, described in Table 5-1.

Subjects will enter the study clinic for check-in procedures the day before study drug administration of the first period (Day -1). All study drugs will be administered subcutaneously. On Day 1, subjects will receive their assigned treatment according to the randomization schedule.

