After the consent process is complete, demographic data, medical history, and concomitant medications will be recorded. A physical examination will be performed by a study team member. Clinical laboratory tests (hematology, serum chemistry, and urinalysis) will be performed. Female subjects must have a negative pregnancy test result. Screening tests will be performed within 21 days of and no later than 2 days before Day 1.

Results of all screening tests will be evaluated by the study clinician/investigator against the inclusion/exclusion criteria to confirm subject eligibility. At check-in, eligibility criteria will be reviewed, any changes in medical history (including concomitant medications) will be documented, vital sign

measurements and a 12-lead electrocardiogram (ECG) will be performed, clinical laboratory, drug and alcohol, and pregnancy tests (for females) will be performed, an intravenous (IV) catheter may be inserted into the subject's forearm region for blood collection (if needed), study drug will be administered, and blood samples will be collected per protocol.

U.S. Food and Drug Administration (FDA) will prepare the randomization schedule. Subjects will enter the study clinic for check-in procedures (Day -1), the day before study drug administration on Day 1. Avonex will be administered intramuscularly and Plegridy will be administered subcutaneously. Placebo will be administered either subcutaneously or intramuscularly to match study drug.

Subjects will be discharged from the study after completion of all study procedures. If a subject discontinues from the study prematurely, all procedures scheduled for the end of the study will be performed. Meal timing and components, activity levels, and general conditions in the study clinic will be as similar as possible on the treatment days.

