### **5.1.2 Dosing Schedule**

- Treatment Group A: Avonex 7.5 µg, IM
- Treatment Group B: Avonex 15 µg, IM
- Treatment Group C: Avonex 30 µg, IM
- Treatment Group D: Plegridy 31.25 µg, SC
- Treatment Group E: Plegridy 62.5 µg, SC
- Treatment Group F: Plegridy 125 µg, SC
- Treatment Group G: Placebo (6 subjects receive IM and 6 subjects receive SC)

Subjects randomized to Treatment Groups A-C will be discharged on Day 7, while subjects randomized to Treatment Groups D-G will be discharged on Day 14. If a subject discontinues from the study prematurely, all procedures scheduled for discharge Day (i.e., Day 7 or Day 14) will be performed.

Safety will be evaluated in terms of AEs, clinical laboratory results (hematology, serum chemistry, and urinalysis), vital sign measurements (blood pressure, heart rate, respiratory rate, and oral body temperature), safety ECG results, and physical examination findings (see Table 9-1).

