### **5.8.6 Blinding**

The pharmacist (and designated staff member responsible for confirmation of study drug dose) will be unblinded to subject treatment assignment; however, the pharmacist will not perform any study procedures other than study drug preparation and dispensing.

Subjects and staff will be blinded to treatment assignment during confinement, but route of administration will not be blinded. The blind will be maintained through a randomization schedule held by the dispensing pharmacist. Subjects and staff will be informed of a subject's end of study day when discharged from confinement. Subjects and staff will not be informed of the specific treatment arm assignment. The clinical research nurse will administer the subcutaneous study drug in unit dose containers that are not transparent.

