### **5.8.7 Treatment Compliance**

At Screening, as part of the inclusion criteria, it will be confirmed that subjects are able to comply with the protocol-defined procedure of injecting subcutaneous study drug. All doses of the study drug will be administered in the study clinic either under direct observation of or administered by clinic personnel and recorded in the eCRF. If a subject vomits after dosing, the event will be documented as an AE. The decision to replace any subject who vomits after dosing will be made as described in Section 5.5.2.

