## Attachment B. Randomization Schedule

Subjects will enter the study clinic for check-in procedures the day before study drug administration of the first period (Day -1). IFN  $\beta$ -1a will be administered intramuscularly and pegIFN  $\beta$ -1a will be administered subcutaneously. Placebo will be administered either subcutaneously or intramuscularly to match study drug. On Day 1, subjects will receive their assigned treatment according to the randomization schedule generated by the randomization biostatistician (unblinded and unaffiliated with study data analysis) and provided to designated unblinded recipients (i.e., pharmacist) at the clinical site.

Treatment Group	Drug
A	Interferon beta-1a (Avonex®) low (7.5 $\mu$ g)
B	Interferon beta-1a (Avonex®) intermediate (15 $\mu$ g)
C	Interferon beta-1a (Avonex®) high (30 $\mu$ g)
D	Peginterferon beta-1a (Plegridy®) low (31.25 $\mu$ g)
E	Peginterferon beta-1a (Plegridy®) intermediate (62.5 $\mu$ g)
F	Peginterferon beta-1a (Plegridy®) high (125 $\mu$ g)
G	Placebo

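### Protocol 5.1.1 gives one route for every study drug and contradicts the dosing sections and SAP Attachment B for 36 of 84 planned subjects (42 if intramuscular placebo counts as study drug)

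*Protocol*

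**What the plan says.** Protocol 5.1.1 (Common Procedures), in the paragraph on check-in and Day 1 treatment, states: "All study drugs will be administered subcutaneously".

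Section 5.1.2 follows directly and gives a route for each group. The Avonex groups read "Treatment Group A: Avonex 7.5 µg, IM", "Treatment Group B: Avonex 15 µg, IM" and "Treatment Group C: Avonex 30 µg, IM". Groups D to F (Plegridy) are listed as subcutaneous, and group G (placebo) as six subjects by each route. Section 5.8.1 repeats this list. The synopsis, under Study Design, says: "Avonex will be administered intramuscularly and Plegridy will be administered subcutaneously". The synopsis entries on study drugs and on the reference drug agree with that, and 5.8.4 repeats the six-and-six placebo split.

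SAP Attachment B also gives Avonex intramuscularly and Plegridy subcutaneously. On placebo it says only: "Placebo will be administered either subcutaneously or intramuscularly to match study drug". It gives no numbers for the split.

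Two other Protocol sections mention one route only. Section 5.8.6 (Blinding) says: "The clinical research nurse will administer the subcutaneous study drug in unit dose containers that are not transparent". Section 5.8.7 (Treatment Compliance) refers to the "protocol-defined procedure of injecting subcutaneous study drug".

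**The concern.** Section 5.1.1 tells the site what to do on Day 1. It gives a single route for all study drugs, while the section after it gives a different route for groups A to C. Either route used in those groups departs from some part of the Protocol, and the supplied text has no rule on which section takes precedence.

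The trial exists to estimate the values and variability of AUEC, maximum change, Cmax and AUC at each dose of each product. Injection route is part of the treatment being characterised. If some subjects in a 12-subject arm were dosed by a different route from the rest, that arm's summary would mix two treatments. SAP Section 5 analyses subjects by the dose and treatment they actually received but does not mention route, so nothing there says how a misrouted subject would be handled. Protocol 8.3.2 counts departures in administering study drug among those that may be significant.

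**Working it through.** **Inputs**
- Seven groups of 12 subjects: Protocol Tables 5-1 and 5-3, SAP Table 1.
- Planned enrolment of 84: Protocol 5.2 and the synopsis.
- Avonex is groups A, B and C, listed as intramuscular: Protocol 5.1.2 and 5.8.1.
- Placebo split of six intramuscular and six subcutaneous: Protocol synopsis, 5.1.2, 5.8.1 and 5.8.4. The split is not in the SAP.

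**Plan's own figure**
7 × 12 = 84, which matches the stated enrolment.

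**Subjects for whom 5.1.1 and the group lists disagree**
- Avonex groups: 3 × 12 = 36; 36 / 84 = 42.9%.
- Adding intramuscular placebo: 36 + 6 = 42; 42 / 84 = 50.0%.
- The other 3 × 12 + 6 = 42 subjects are listed as subcutaneous, so 5.1.1 does not conflict for them.

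The range comes from what the term study drugs covers. The synopsis lists only Avonex and Plegridy under that heading and puts placebo under the reference drug, which gives 36. Section 5.8.1 lists placebo among the seven treatments and then calls them study drugs collectively, which gives 42. Both counts use the planned 84 and exclude replacements.

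**Passages side by side**

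| Place | Avonex | Plegridy | Placebo |
|---|---|---|---|
| Protocol 5.1.1 | SC | SC | SC, if a study drug |
| Protocol synopsis | IM | SC | 6 IM, 6 SC |
| Protocol 5.1.2 | IM | SC | 6 IM, 6 SC |
| Protocol 5.8.1 | IM | SC | 6 IM, 6 SC |
| Protocol 5.8.4 (planned placebo injections) | – | – | 6 IM, 6 SC |
| SAP Attachment B | IM | SC | Either, no split given |

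Only 5.1.1 gives a single route for everything. Section 5.8.6 also leaves the route unmasked, which presupposes more than one route.

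**Likely origin**
The paragraph in 5.1.1 refers to a first period, although this is a single-dose parallel trial. SAP Attachment B opens with nearly the same paragraph, including that reference, but carries a two-route sentence where 5.1.1 has its single-route one. That pattern points to carried-over text. It is an inference, and the sponsor would have to confirm it.

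**The case against.** The strongest case against is that this is one generic sentence set against several specific and consistent ones. Section 5.8.1 is the section on treatments administered and gives a route for every group. Section 5.1.2 does so immediately after the disputed sentence. The next sentence in 5.1.1 sends staff to the randomisation schedule. A site would have to overlook all of this to act on 5.1.1 alone. This argument stands as far as the likelihood of error goes. It does not make the sentence correct, and a Day 1 administration instruction should not depend on staff working out which sentence to ignore.

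A reader might infer four stronger things that the documents do not support:

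- **That the contradiction runs through three sections.** Section 5.8.6 describes how the subcutaneous drug is handled, and 5.8.7 is a loosely worded statement about ability to comply. Neither says that all drugs are subcutaneous. Their silence on the other route is a gap in wording. In 5.8.6 it is a small masking point, and the opaque container is not the only protection: a separate unblinded pharmacist prepares the doses, and placebo matches the high-dose volume.
- **That half the trial is affected without qualification.** The 50.0% figure requires counting placebo as a study drug.
- **That the SAP assigns half of placebo intramuscularly.** Only the Protocol states the split.
- **That the Avonex results would be invalid.** That would require misrouting to occur and to matter. The documents give no figure for a route effect.

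**Conclusion.** The contradiction is real. It is in current text and within the Protocol itself, and SAP Attachment B also disagrees with 5.1.1. It covers 36 of 84 planned subjects, or 42 of 84 if intramuscular placebo counts as study drug. These figures count subjects under conflicting instructions; they do not estimate how many would be misdosed, which is probably few or none given the consistent lists elsewhere. The carry-over explanation is likely but unconfirmed.

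It should be corrected because it is a contradictory administration instruction in an operative section and is cheap to repair. The wording in 5.8.6 and 5.8.7 is secondary. This review takes no position on which route is right.

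**What to change.** Reconcile the sentence in 5.1.1 with the synopsis, 5.1.2, 5.8.1, 5.8.4 and SAP Attachment B, so that the route or routes for each group are stated identically wherever they appear. Group G has two routes by design, so the aim is matching statements, not a single route per group. The numerical placebo split could be added to SAP Attachment B so that it matches the Protocol.

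In the same correction, word the container text in 5.8.6 and the compliance text in 5.8.7 to cover every route used.

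The cost is about one sentence for the contradiction and one each for 5.8.6 and 5.8.7, in an amendment or clarification. It needs no extra subjects or procedures and changes no analysis.
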